Pre-screening: Interested individuals will be provided with a brief description of the study and prescreened via brief telephone interviews. This prescreening interview will inquire about basic demographic information (e.g., name, age, sex), inclusion and exclusion criteria. Those meeting entry criteria will be invited to participate, and an appointment date/time will be arranged.

During Visit 1, at Butler Hospital, participants will provide information about demographics, complete safety screening for MRI and CES as well as complete self-report questionnaires, including the PTSD Checklist for DSM-5 (PCL-5) [20] to assess self-report severity of PTSD symptoms; the Inventory of Depressive Symptoms, Self-Report (IDS-SR) [21] to assess self-report depression severity; the State-Trait Anxiety Inventory (STAI) [22] to evaluate self-report symptoms of anxiety; the Pittsburgh Sleep Quality Index (PSQI) [23] to assess subjective quality of sleep prior to CES use. The Quick Structured Clinical Interview for DSM-5 (QuickSCID) [24] will also be administered by a trained evaluator to assess for general psychiatric diagnoses and exclusion criteria. Finally, participants will be trained in how to complete EMA assessments, as well as use the Oura ring if applicable.

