Cranial electrotherapy stimulation (CES): We will use the Alpha-Stim AID device for CES following device instructions. The Alpha-Stim AID CES device has FDA clearance for treatment of anxiety and/or insomnia. During CES participants will have two ear clips attached to either ear to provide stimulation. Prior to placing the ear clip on each earlobe, participants will wipe their earlobes with an alcohol wipe and let them dry. These ear clips each include an electrode pad that will be moistened with the provided Alpha-Stim conducting solution until they are thoroughly saturated. Participants will then turn on the device, set the timer to one hour, and place each pre-wetted ear clip on their ears. CES includes a modified square, bipolar waveform of 0.5 Hz at 10-500 μ A intensity, that will be individually adjusted to be below the threshold of mild tingling sensations and/or dizziness following device manufacture guidance and prior research [25]. Specifically, intensity will be individually set by asking participants to increase the current until a slight dizzy feeling is experienced, then decrease immediately until the dizziness stops. This individual adjustment of intensity will occur during the first study visit at Butler Hospital under the guidance of study staff. Study staff will go over the device manual, guide participants throughout the entire device set-up, and observe a practice CES session to

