ensure participants understand all procedures as well as assess tolerability of the individually determined stimulation intensity prior to sending participants home with the Alpha-Stim AID CES device. The device manual, a quick set-up guide for ease of reference, as well as information on the determined intensity and a pen-and-paper tracking log will be provided to participants to be used during the four-weeks of at home administered CES. Throughout the four weeks of CES, participants will be asked to document the day, time, and duration of CES application using the provided tracking log. Participants will be instructed to only use the Alpha-Stim AID CES device on 'off-duty days' (i.e., days on which they are not working). This is done as an extra precaution to avoid potential negative effects of CES on work-related performance as using heavy machinery immediately following CES is not advised per device manufacturer. The research team will check in with the participant at least once per week (or more often if indicated based on incomplete EMA surveys or difficulties using the CES device), during the four weeks of CES, starting on the second day after starting CES. This check-in will allow obtaining feedback on user feasibility as well as allow assessment for the presence of side effects/adverse events. We will use a recently adapted Side Effects Questionnaire based on the one developed by Brunoni and colleagues [26]. Participants will also be provided with a contact phone number in case they experience side effects/adverse events prior to study staff check-ins or in case questions or other issues arise. Participants will be reminded that if they experience vertigo (a dizzy feeling, similar to the sensation of rocking on a boat) despite the predetermined intensity set during the in-person visit at Butler Hospital, they should decrease the intensity immediately until the dizziness stops.

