- (5) CES: CES is considered a low-risk technique that is well tolerated and carries minimal to no side effects. CES devices are FDA cleared as Class II devices. The to-be-used CES device (AlphaStim AID) can be purchased online by individuals from the company website (for US customers a 'doctor's note' is required but this can be arranged online on the company website at time of purchase – in the proposed study, release of the device to participants will be provided by physicians in Butler's Neuromodulation Research Facility, following company purchasing practices). Side effects from CES are mild and self-limiting (<1%). The most common side effects include vertigo, nausea, and headache [16, 25], although skin irritation at electrode sites, ear pain, tingling, pulsing or tingling sensations on ears, and tender ears have also been reported. In a large trial in 115 participants with anxiety disorder and comorbid depression reported no adverse events using the Alpha-Stim CES device we propose to use in the current study and with identical settings [27]. CES is thought to be safe without risk of seizure induction in the absence of neurologic risk factors. CES is contraindicated with implanted pacemakers or implanted or wearable defibrillators and pregnancy as safety of stimulation has not been established during pregnancy. It is advised not to use dangerous machinery or vehicles during treatment, and in some cases following treatment.
- (6) EMA: EMA surveys might be frustrating because they ask the same things multiple times. EMA survey notifications delivered during working hours can cause distraction.
- (7) Oura ring: The Oura ring is made from metal and as with any ring, skin irritations or difficulty removing the ring can occur. The Oura ring contains a battery, and when working with batteries, or devices and/or with machinery that contain batteries while wearing the Oura ring, there is a risk of a short circuit when both the cathode and the anode of another battery touch the ring. This can result in a potentially dangerous shock. The Oura is a radio transmitter and receiver. It's designed not to exceed the emission limits for exposure to radio frequency (RF) energy set by the Federal Communications Commission. Ring EMF frequency has an SAR (Specific Absorption Rate) level of 0.0003 W/kg, compared to an SAR level at or below 1.6 W/k for all cell phones sold in the United States.

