- (5) CES: To minimize risks due to CES, all participants will be carefully screened for contraindications to CES as listed in the exclusion criteria. As the risks of CES during pregnancy are unknown (although most likely not harmful), pregnant individuals are excluded from participation based on historical guidelines. Use of an electrically isolated power source (i.e., battery-powered stimulation device) also protects against delivery of more intense currents than intended. Stimulation parameters (current and frequency) will be preset and tested for tolerability during Visit 1 under the guidance of Drs. [REDACTED] [REDACTED]. Participants will be told that modification of the Alpha-Stim device or accessories is not allowed, and that doing so could result in injury. They will also be told to not stimulate directly on the eyes or press the probes over the carotid sinus (on the neck near the larynx) and application of the electrodes near the thorax may increase the risk of cardiac fibrillation, as well as that it is advised to not use dangerous machinery or vehicles during treatment days, and that for that reason CES should only be applied/used on off-duty days or after completion of a duty cycle. Participants will have the option of discontinuing the study at any time and will be explicitly instructed to contact the research team if they experience any discomfort. The research team will reach out to participants at least once per week during the four weeks of CES (or more often if indicated based on incomplete EMA surveys or difficulties using the CES device). To assess for presence of adverse events, we will use a recently adapted Side Effects Questionnaire based on the one developed by Brunoni and colleagues [26]. If there is any doubt about the mental or physical status of an individual during the CES intervention, participants will be evaluated by Dr. [REDACTED] in her role as clinical psychologist, who will make recommendations for follow-up care, if required. Telephone or in-person follow-up will be arranged as needed and will not be considered a protocol deviation. Any participant judged on clinical grounds to have suffered adverse effects will thus be evaluated and treated as necessary and withdrawn from the study if deemed necessary.

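### No pre-CES administration of the Side Effects Questionnaire is specified, so in this single-arm study complaints that predate CES are harder to tell from CES side effects

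*Combined protocol and SAP*

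**What the plan says.** The questionnaire appears in two places.

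- **C3, Cranial electrotherapy stimulation (CES).** Staff contact participants at least weekly "during the four weeks of CES, starting on the second day after starting CES". The contacts gather feedback on use "as well as allow assessment for the presence of side effects/adverse events". The next sentence names the instrument: "We will use a recently adapted Side Effects Questionnaire".
- **Human Subjects, D1 (5) CES.** After again describing at-least-weekly contact during the CES period, the text says "To assess for presence of adverse events, we will use a recently adapted Side Effects Questionnaire".

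The visit descriptions do not mention it.

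- **C3, Visit 1.** Here "participants will provide information about demographics, complete safety screening for MRI and CES as well as complete self-report questionnaires". The measures named are the PCL-5, IDS-SR, STAI and PSQI, followed by the QuickSCID interview.
- **C3, Visit 1 practice session.** Intensity is set by asking participants to "increase the current until a slight dizzy feeling is experienced, then decrease immediately until the dizziness stops". Staff then observe a practice session and "assess tolerability of the individually determined stimulation intensity prior to sending participants home". No instrument is named for this check.
- **C3, Visit 4.** Self-report measures from Visit 1 are repeated and a debriefing is held.

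C2 describes one group in which everyone receives CES in the same way. Human Subjects, C (5) gives the expected effects: "Side effects from CES are mild and self-limiting (<1%). The most common side effects include vertigo, nausea, and headache".

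**The concern.** The effects expected of CES are symptoms that people also have without it, and C3 notes that these participants may work night shifts. A trial with a sham arm could compare rates between arms. This one has only the participant's own earlier state. The study already applies that logic to PTSD symptoms, depression, anxiety and sleep, which are all measured before and after CES. Side effects are the exception.

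Without a prior score on the same items, a headache that a participant has carried for months may be recorded at a check-in as a side effect, or set aside as old on the strength of recall. Either way the tolerability description is biased, and the study is meant to inform the design of a later trial. A baseline also cannot be recovered once a participant has been stimulated, and the first stimulation is at Visit 1, not at home.

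**Working it through.** **1. Where a pre-CES score could be found.** Each place that mentions side effects, adverse events or a visit battery was checked.

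| Place | Before first stimulation? | Same symptom items? |
|---|---|---|
| C3 check-ins | No; from the second day after starting CES | Yes |
| D1 (5) | No; named with the contacts during CES | Yes |
| Visit 1 battery | Yes | Questionnaire not listed |
| Visit 1 practice session | No; concerns the response to current | No instrument named |
| Visit 4 | No | Questionnaire not listed |
| EMA | No; runs during the CES period | No; affect, fatigue, stressful events |
| D1 (9) | Mentions evaluation before and after CES | Side-effect monitoring is placed in the four weeks of CES |

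No row supplies a specified pre-CES score on these items.

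**2. The plan's own figure.** C2 wants 16 participants with data after 20% attrition: 16 / (1 − 0.20) = 20, as stated. A baseline form changes nothing here.

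**3. Scale if complaints persist.** Let p be the share of participants with a continuing complaint that predates CES. The documents give no value, so 5% to 20% is assumed. Reports at check-ins with no CES effect are 20 × p:

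- p = 0.05: 1 of 20
- p = 0.10: 2 of 20
- p = 0.20: 4 of 20

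A Visit 1 form would show these as already present, unless they later worsened.

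**4. Scale if symptoms are episodic.** Now let p be the chance of a report at any one check, independent over four weekly checks. The share reporting at least once is 1 − (1 − p)^4. The share absent at Visit 1 but reported later is (1 − p)[1 − (1 − p)^4].

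| p | At least one report | Still labelled new after one baseline |
|---|---|---|
| 0.05 | 18.5% (3.7 of 20) | 17.6% (3.5 of 20) |
| 0.10 | 34.4% (6.9 of 20) | 31.0% (6.2 of 20) |
| 0.20 | 59.0% (11.8 of 20) | 47.2% (9.4 of 20) |

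Under independence, one baseline removes only the fraction p of the reporters. Step 3, not step 4, is therefore the right measure of what the baseline can do.

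**The case against.** The strongest reply is that the documents are silent here, and silence is not a plan to omit. The second-day timing describes the check-ins, and the sentence naming the questionnaire carries no timing of its own. The lists of measures at Visits 1 and 4 are worded as examples or partial lists. D1 (9) refers to evaluation before CES. D3 sends detailed operating procedures to a binder that is not among the documents. This stands: a reader might infer that the form is definitely first given after CES has begun, but the text supports only that no earlier administration is specified.

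A reader might also infer that old complaints and CES effects cannot be separated at all. That goes too far. The session log records day, time and duration of use, ongoing medical care is recorded, and unstable illness and several neurological conditions are excluded. The form's items are not shown, so it may ask about onset or relatedness. These are partial aids, and none is known to be a pre-CES score on the same items.

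A third tempting inference is that misattributed side effects distort attrition, where one withdrawal is 5 points of 20. Attrition counts a withdrawal whatever its attributed cause, and a baseline form would not change who is counted.

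A fourth is that the study could not check the quoted rate of under 1%. That figure is background in the risk section, and no aim or C4 analysis tests it. Even with a perfect baseline, a 1% rate implies 0.2 events in 20 participants and a chance of 1 − 0.99^20 = 18% of seeing any.

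**Conclusion.** The point holds as a gap in the specification of secondary tolerability data. No pre-CES administration of the Side Effects Questionnaire is specified and there is no control arm, so persistent complaints that predate CES are harder to distinguish from side effects. The size is illustrative: 1 to 4 of 20 participants if 5% to 20% have such a complaint, a range that is assumed and not drawn from the documents. The larger shares in the episodic calculation, 18.5% to 59.0%, should not be read as the size of the problem. They rest on assumed rates and on independence between checks, and one baseline would leave most of them in place. Sessions completed, attrition and the sample size of 20 are unaffected. This is a cheap improvement, not a threat to Aim 1.

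**What to change.** - In C3, Visit 1, add the same Side Effects Questionnaire, completed before intensity-setting and the practice session, since that is the first CES exposure.
- In C3, Visit 4, add it again.
- In C4, add one sentence: side effects will be reported both as all reports and as items new or worse than at Visit 1.
- If a Visit 1 administration is already intended or sits in the operating procedures, say so in C3 and state that it precedes stimulation.

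The cost is a few minutes of participant time at two existing visits, with no new staff, visit or change in sample size. Its limit is that a single baseline will not remove most episodic background symptoms, which is why both sets of figures should be reported.

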COVER PAGE – STUDY PROTOCOL

Title: Cranial electrotherapy stimulation: Piloting a road to PTSD prevention in first responders

NCT number: NCT06203717

Document date: 08/15/2024

BUTLER HOSPITAL
INSTITUTIONAL REVIEW BOARD
PROTOCOL

Project**Title of Project:** Cranial electrotherapy stimulation: Piloting a road to PTSD prevention in first responders**Short Title of Project:** CES in firefighters**Principal Investigator (PI):** [REDACTED]**Other Investigator(s):** [REDACTED]**Revision History:**

Version Number	Version Date	Summary of Revisions
1.0	08/28/2023	First version submitted
	09/18/2023	First version approved
2.0	12/14/2023	
 1. Changed PI from [REDACTED]. 2. Added [REDACTED] as co-investigator to the study team. 3. Corrected error in ecological momentary assessment (EMA). 4. Added new advertisement material.
3.0	05/28/2024	
 1. Revised CNE Research Application to change Device Risk Level to "nonsignificant risk device" instead of "N/A". 2. Updated protocol to include XNAT – a password protected secure server – for transfer of MRI data from MRF to Butler. 3. Broadening of recruitment locations to include community locations (e.g. coffee shops).
4.0	8/15/24	
 1. Broadening of recruitment methods through social media marketing. 2. Update protocol to allow for texting for initial outreach to potential participants.

Description of Study**A. Specific Aims**

Aim 1: Test the feasibility and acceptability of Cranial electrotherapy stimulation (CES) in firefighter first responders.

Prediction: CES is feasible quantified as more than 75% of sessions completed, and acceptable quantified as less than 20% attrition in the sample, such that at least 16 out of 20 firefighters complete, for example, at least 15 out of 20 sessions over the course of four weeks.

Aim 2: Test the effects of CES on subjective homeostatic functioning in firefighter first responders.

Prediction: CES will reduce subjective fatigue and frequency and intensity of negative emotions (e.g., distressed, nervous) while increasing the experience of positive emotions (e.g., calm, inspired) assessed naturalistically in near real-time through ecological momentary assessments (EMA).

Aim 3: Test the effect of CES on objective homeostatic functioning in firefighter first responders.

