Critical Gaps in Knowledge. Despite CES' potential for use in first responders, there are no studies that evaluate if a predefined four-week course of CES is feasible and acceptable in firefighters. Although one study examined CES in a sample of 86 first responders consisting mainly of law enforcement as well as 10 firefighters, participants were "permitted to use the device any time of day and for any indication" [c.f. 17] and the report does not mention of how often, at what time of day, and for how long participants used the device or whether

there were difficulties with its use, providing no information about feasibility or acceptability. This is important because it is advised to avoid the use of heavy machinery after CES. Therefore, the application of CES should be carefully integrated with the firefighter work schedules, starting with its use only on off-duty days.

Additionally, there are no studies that test the effects of CES on subjective and objective indices of homeostatic functioning in active-duty firefighters to gain insight into possible mechanisms of CES-modulatory effects. In fact, despite a literature on effectiveness for anxiety, insomnia, and depression [but see 18 for a negative randomized controlled trial], the mechanism of CES effects on homeostatic functioning remains rather hypothetical with little direct evidence [19].

Here we propose to address these critical gaps in science by testing if a course of four weeks of CES in firefighters is 1) feasible and acceptable in this population; 2) impacts subjective variables associated with homeostasis, including fatigue, frequency and intensity of negative and positive emotions (i.e., distressed, nervous, calm, inspired); and 3) changes objective variables associated with homeostasis, including functional and structural neural connectivity, heart rate variability, and sleep quality in a subset of participants.

C. Experimental Method

C1. Brief Description of Subjects

Participants will be 20 active-duty firefighters in the State of Rhode Island, between 18-56 years old.

Participants will be of any racial or ethnic group and of any gender.

C2. Study Design

This study will use a within-subject design, with all participants completing all experimental procedures with no difference to how CES will be applied. Recruitment of 20 participants incorporates an estimated 20% attrition to allow data collection on 16 participants.

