The Project Leaders of this supplement, [REDACTED] will be responsible for and supervise data collection and data management. The main goals of this study involve assessing feasibility (i.e., > 75% of CES sessions completed) and acceptability (i.e., < 20% attrition in the sample) of a 4-week course of CES in active-duty firefighters (i.e., at least 16 out of 20 firefighters complete at least 15 out of 20 sessions over four weeks) and obtaining preliminary signal of effect to inform the design of a future, collaborative clinical trial to test efficacy of CES for the prevention of PTSD in first responders. Our primary outcome measures include the number of completed sessions to quantify feasibility and attrition in the sample assessing acceptability (Aim 1). In addition, we will collect data on subjective fatigue, negative and positive emotions using ecological momentary assessment (Aim 2) as well as heart rate variability and sleep quality (Aim 3). Finally, we will collect pre- and post-CES data on clinical symptoms (PTSD, depression, anxiety) and MRI-based resting state functional connectivity and structural connectivity (Aim 3). Given the preliminary nature, the proposed study is not designed to have adequate power to robustly test whether CES is effective for PTSD prevention, which would constitute the long-term goal of the proposed work. As such the proposed number of 20 individuals is solely meant to achieve the listed aims.

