Data will be analyzed through t-tests and general linear models (e.g., (M)AN(C)OVA, repeated measures analyses, linear mixed models) using statistical software (e.g., SPSS, R, MPlus). To maintain anonymity in data files participants will only be listed with their unique identification code. Data backup of these files and hard copies of data capture forms will be kept in locked files to which only authorized study personnel will have access. Descriptive data will be provided for all participants (e.g., mean age, sex, education, etc.). Clinical rating scales will be scored as they are in clinical use. Interpretation of results will adjust for multiple testing to account for false discovery rates using step-down procedures where appropriate [87, 88]. EMA data will be aligned through a timestamp, permitting time parameterization of statistical models. Oura ring data is preprocessed by internal Oura algorithms (e.g., average HRV, Sleep score: REM, latency, deep sleep, restfulness) for comparison over time. All data will be examined for patterns and mechanisms of missingness prior to analyses to ensure missing data approaches are appropriate. For EMA data, we will use Blimp 2.1 to conduct multiple imputation for multilevel missing data prior to analyses. Multiple imputation using a Bayesian estimation approach or via full information maximum likelihood will be implemented as necessary for non-ecological data.

Electronic and/or digitized data (including PHI) will be stored on a password-protected server at Butler Hospital (e.g., COBRE), at the University of Rhode Island, and in CNE REDCap. This study will use Care New England's instance of REDCap for collection and storage of data. The study will not collect or store any actual data within REDCap until the project has been moved into REDCap's production environment. REDCap is a secure, web-based application developed by Vanderbilt University for building and managing surveys and databases. It is primarily designed to support online or offline data capture for research studies, quality improvement, and operations. REDCap provides easy data manipulation (with audit trails for reporting, monitoring and querying patient records), real-time data entry validation, and an automated export mechanism to common statistical packages. When data is downloaded, PHI will be removed and only an assigned code number will remain for analysis.

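### Aim 1 is decided by a raw count from 20 people against an inconsistently stated cut-off, with no interval planned for the proportions

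*Combined protocol and SAP*

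**What the plan says.** **Recruitment.** Section C2 (Study Design) states: "Recruitment of 20 participants incorporates an estimated 20% attrition to allow data collection on 16 participants".

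**Success rule.** Section A (Specific Aims) calls CES "acceptable quantified as less than 20% attrition in the sample, such that at least 16 out of 20 firefighters complete" a given number of sessions, with 15 of 20 offered as an example. Section C4 (Data Analysis) repeats the bound as "acceptability (i.e., < 20% attrition in the sample) of a 4-week course of CES in active-duty firefighters" and restates it as "at least 16 out of 20 firefighters complete at least 15 out of 20 sessions over four weeks". Feasibility in both sections is more than 75% of sessions completed. C4 names the number of completed sessions and attrition as the primary outcome measures.

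**Analysis.** C4 says "Data will be analyzed through t-tests and general linear models". It goes on to mixed models, adjustment for multiple testing, and imputation. It gives no confidence interval, test, reference rate or precision target for the Aim 1 proportions, and no other section does.

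**The concern.** Three features combine. The acceptability bound equals the attrition allowed for in recruitment. The decision is a comparison of an observed count with that bound. Nothing in the plan expresses how uncertain a count out of 20 is.

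The wording of the rule adds to this. If attrition is exactly what C2 allows for, 16 people remain. That is the one count on which the two statements of the acceptability rule disagree: it satisfies at least 16 of 20 and fails attrition below 20%.

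At stake is what the primary outcome can tell the designers of the later trial that C4 says this study will inform. They need a plausible range for attrition and adherence, and a bare pass or fail does not give one.

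**Working it through.** **Inputs.** 20 recruited, 20% attrition and 16 remaining (C2); attrition below 20%, at least 16 of 20 firefighters, more than 75% of sessions, and at least 15 of 20 sessions (A and C4). The documents give no confidence level for Aim 1; two-sided 95% is assumed here.

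**1. The plan's own figure.** 16 / (1 − 0.20) = 20. The recruitment number is reproduced.

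**2. The two forms of each rule.**
- Attrition: 16 of 20 retained means 4/20 = 20% lost, which is not below 20%. Attrition below 20% allows at most 3 losses, so it needs 17 of 20.
- Sessions: 15/20 = 75%, which is not more than 75%. A participant needs 16 of 20 sessions to exceed it.

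**3. What an observed count supports.** Exact (Clopper-Pearson) limits for x of n = 20: the lower limit is the 0.025 quantile of Beta(x, n − x + 1); the upper limit is the 0.975 quantile of Beta(x + 1, n − x). Attrition limits are 100% minus the retention limits.

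| Retained | 95% CI, retention | 95% CI, attrition |
|---|---|---|
| 16/20 | 56.3% to 94.3% | 5.7% to 43.7% |
| 17/20 | 62.1% to 96.8% | 3.2% to 37.9% |
| 18/20 | 68.3% to 98.8% | 1.2% to 31.7% |
| 19/20 | 75.1% to 99.9% | 0.1% to 24.9% |
| 20/20 | 83.2% to 100% | 0% to 16.8% |

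Only 20 of 20 puts the whole interval on the favourable side of 20% attrition. A Wilson interval for 16/20, as a check, is 58.4% to 91.9%.

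**4. How often the count is met.** With independent participants and common retention p, P(X ≥ r) = Σ C(20, k) p^k (1 − p)^(20 − k), summed over k = r to 20. At p = 0.80 the terms for k = 16 to 20 are 0.2182, 0.2054, 0.1369, 0.0576 and 0.0115. They sum to 0.630 from k = 16 and to 0.411 from k = 17.

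| True attrition | At least 16 of 20 | At least 17 of 20 |
|---|---|---|
| 10% | 0.96 | 0.87 |
| 15% | 0.83 | 0.65 |
| 20% | 0.63 | 0.41 |
| 30% | 0.24 | 0.11 |

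At 20% attrition the choice between the two stated rules moves the chance of success by 0.630 − 0.411 = 0.219, about 22 percentage points.

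**5. Session rate.** Sessions cluster within people, so the unit for an interval is the participant. With one completion percentage per person, the 95% half-width is t(0.975, 19) × SD / √20 = 2.093 / 4.472 × SD = 0.468 × SD. The documents give no SD, so no numerical width is claimed.

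**The case against.** **It is a small pilot, and a descriptive count is enough.** C4 does describe the study as preliminary, and a count with its denominator is not misleading in itself. But the disclaimer of power in C4 concerns efficacy for PTSD prevention. The same paragraph says the 20 participants serve the listed aims, and Aim 1 is the first of these. An interval needs no power and no extra participants. The objection limits the weight of the point without removing it.

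**The 20% is an allowance, not a forecast.** This stands in part. A reader might infer that, by the plan's own estimate, the verdict is near a coin toss, since the two rules give 0.63 and 0.41 at 20% attrition. C2 does use the word estimated, but its purpose there is to leave enough participants: "to allow data collection on 16 participants". Section A predicts attrition below 20%. At 15% or 10% the 16-of-20 count is met with probability 0.83 or 0.96. The documents do not fix 20% as the expected rate.

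**The joint requirement makes success much less likely still.** A reader might multiply 80% retention by some share of retained participants who reach 15 sessions. The documents give no such share. The wording in Section A can also be read as making the session count the meaning of completing, in which case the 20% already covers those who fall short and the product would discount them twice.

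**Intervals are already covered by the listed methods.** This is partly right. A t interval on sessions completed per participant falls within the t-tests C4 names, although C4 does not say it will be reported. It does not cover the proportion retained or the proportion reaching the session minimum.

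**Conclusion.** The point holds as one of reporting and definition for the primary outcome. A pass at 16 of 20 is compatible with true attrition of up to about 44%, and a pass at 17 of 20 with up to about 38%. At a true attrition of 30% the count is still met 24% of the time under the 16-of-20 rule and 11% under the 17-of-20 rule. The two forms of the acceptability rule disagree at exactly the count C2 plans for, and the two forms of the session rule disagree at exactly 15 of 20.

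These figures assume independent participants with a common retention rate, all 20 in the denominator, and a 95% level chosen here. They do not show that the sample is too small for a pilot or that the criterion is likely to fail. A reader might also infer that a bare pass would be taken into the next trial as settled. The documents do not support that: they contain no go/no-go rule, and C4 says only that the study will inform a later design.

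This is a cheap improvement that limits what can be concluded; it does not call for a redesign.

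**What to change.** In C4, and in the Aim 1 prediction in Section A:

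1. Reconcile the two forms of the attrition bound and the two forms of the session bound, so that each has one stated rule.
2. Report the number retained, and the number reaching the session minimum, out of all 20 enrolled, each with an exact (Clopper-Pearson) 95% CI.
3. Report the session completion rate with a CI computed across participants.
4. Word the result as criterion met, or not met, in this sample, and give the interval beside it.

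The cost is a few sentences in the plan and a few lines of analysis, with no more participants or data. The downside is a more guarded conclusion on feasibility and acceptability.
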